Northwestern University. Division of General Internal Medicine and Geriatrics, Institute for Healthcare Studies, Feinberg School of Medicine, Northwestern University, [name]. Northwestern Medicine, led by Site PI [name]., M.P.H., FACP and Co-I [name]., M.P.H., will be the clinical site for Randomized Controlled Trial implementation. Drs. [name] and [name] will work with the overall study investigators to conduct the specific aims of this study. [name] and [name] will ensure the NU Analyst is able to extract necessary data from the electronic health record for analytic purposes. Throughout the project, [name] and the others will work with the overall project team to disseminate the results of such development, implementation, and evaluation. They will participate in regular project meetings with the entire study team via teleconferencing and at in person meetings and will prepare scientific publications and presentations along with the other members of the study team.

University of Washington: [name] is Co-Investigator and subcontract PI for University of Washington. In his role on this project, he will assist in study design, provide expertise in the implementation of PainTracker, and the analysis and interpretation of outcome data. He will participate in regular project meetings with the entire study team via teleconferencing and at in person meetings and will prepare scientific publications and presentations along with the other members of the study team.

PRÉCIS

Study Title

Guiding aging long-term opioid therapy users into safer use patterns

Objectives

The main objective is to use of point-of-care randomization within the electronic health record to learn if different survey assessments lead to different medical decisions and patient care pathways that will improve the health services received by long-term opioid therapy recipients. We develop strategies for comparison for collecting clinical pain data and for assessing, preventing, and managing pain in later life. Our intent is also to elucidate at the visit, some of the psychosocial factors underlying pain experience and its consequences in aging. We utilize the UW PainTracker, a brief assessment that reframes the patient visit around improving function and identification of correlates of pain intensity to broaden the discussion around patient needs to address chronic pain in an aged population.

Design and Outcomes

Using the electronic health record, patient portal, and patient-reported outcome capabilities, we will develop programming logic for a randomized experimentation platform wherein two (or more) versions of pain surveys may be delivered to patients. In a randomized controlled trial, we will use this system to evaluate Current Opioid Misuse Measure (COMM) + PainTracker¹⁵ delivered randomly to half of persons over 65 years of age on long-term opioid therapy within patient registries at Northwestern University's health system with at least one primary care encounter in the past 12 months. The other half of patients receive standard clinical practice at Northwestern which involves assessment with COMM only which focuses on identifying opioid misuse and abuse, but not broader problems associated with chronic pain.

Interventions and Duration. The intervention period will be 9-months in length for all participants. The following intervention arms will be compared:

Condition 1 (Current Opioid Misuse Measure) - On a monthly basis, as part of standard clinical practice, patients will receive the Current Opioid Misuse Measure, a 17-item self-report screener to identify and monitor the risk of aberrant opioid-related behavior in chronic pain patients on opioid therapy. The COMM asks patients to report their behaviors over the past 30 days using a five-point Likert-type rating scale. Multiple studies have shown that the COMM can accurately identify patients who are engaging in aberrant opioid-related behavior (defined as medication misuse, abuse, addiction, diversion, and opioid-seeking behaviors) with approximately 80% accuracy.

Much of its classification accuracy is because many of the items, while predictive of opioid misuse, do not appear to patients to be asking about opioid misuse.

Condition 2 (Current Opioid Misuse Measure+ PainTracker) - On a monthly basis, patients will receive both the Current Opioid Misuse Measure (described above) and PainTracker. The latter tracks multiple outcomes relevant to the treatment of chronic pain: pain severity, general activity interference, enjoyment of life interference, sleep (initiating and maintaining), depression, and anxiety. New and returning patients are asked to complete the PainTracker assessment at least one week prior to their appointment.

Outcome Measures: We will assess the primary outcome in the electronic health record: referral rate to non-opioid related care, which includes mental health, physical therapy and sleep medicine referrals. We will also measure the rate of new starts on antidepressants. Secondary outcomes include: 1) clinician aggregate monthly milligram (mg) morphine equivalent (ME) and 2) benzodiazepine prescribing.

1. STUDY OBJECTIVES

1.1 Primary Objectives

The primary objective is to assess the comparative effectiveness of PainTracker in a randomized controlled trial at Northwestern Medicine in the United States.

2. BACKGROUND AND RATIONALE

2.1 Background on Condition, Disease, or Other Primary Study Focus

Over the last two decades, prescription opioids have grown to become a public health crisis. Today, on average 1 in 5 persons with chronic noncancer pain receive an opioid prescription in the U.S.¹ Yet, despite this record level of prescribing, reports of pain in America have not gone down.^{2,3} The greater availability of prescription opioids has been accompanied by an alarming rise in the negative consequences related to their use. In 2015, there were over 365,000 emergency department visits for misuse and 20,101 prescription overdose deaths, more than have ever been recorded in U.S. history.^{4,5} The costs of prescription opioids are staggering. Aggregate costs for prescription opioid harm are estimated at over \$78.5 billion (in 2013 dollars). One-fourth of the aggregate economic burden is publicly funded (i.e., Medicaid, Medicare, and veterans' programs).^{6,7}

While there have been reductions in opioid prescribing, persons 65 years of age and older who take these medications continue to face particular risks. First, these persons are more likely to have started on long-term opioid therapy in the early 2000s for non-progressive musculoskeletal pain conditions and continue on opioids to this day. These are “legacy patients” with chronic pain who progressively escalated to high opioid doses, often over many years. Now as they age, they face additional and very serious risks resulting from continued use. Age-related changes in drug metabolism, multi-morbidity, and polypharmacy place them at risk of falls and death due to respiratory suppression.

The dominant approach to these risks is to screen for aberrant patient opioid behaviors so that clinicians can pre-empt misuse early through review of contractual opioid agreements or by lowering patient dosages.^{8–11} This approach fails the patient in several ways. First, it frames the clinician's judgment task solely as one of determining if the patient is likely a misuser without examining the reasons for misuse. In older patients, control of physical pain is the most common reason for opioid misuse.¹² Labeling patients as misusers can reduce doctor and patient trust, which can hamper future interactions necessary for future care. Second, it ignores situational and

psychological factors associated with high-dose opioid use. By focusing on opioid misuse alone, it encourages forced opioid tapering that has been associated with opioid overdose and mental health crisis.¹³ Many persons have mental health, trauma-related or polysubstance use disorders that need to be addressed. Directing clinician attention to these comorbid conditions associated with opioid misuse may promote safer and more effective care.

Making these situational and psychological factors more salient may reframe the problem for the physician and patient in a number of productive ways. First, psychological studies of similarity find that an increase in the measure of common features increases the perception of similarity and decreases the perception of difference.¹⁴ The more features of misuse that the survey assessment requires, the greater the perceived similarity the patient has to a referent person who misuses or abuses drugs. Also, an increase in the measure of the distinctive features decreases similarity and increases difference. The more the physician measures the patient's activity limitation, mental health issues, and reactions to traumatic stress, the less likely physicians might be to view the patient as a wrongdoer and more likely to open up new care pathways (e.g. physical therapy, mental health referrals, and sleep medicine) that may improve their condition. In sum, understanding broadly, a patient's pain experience may help address the reasons why these patients use opioids and may prevent problem use. This is superior to simply identifying persons who misuse medication. For 12 years, our team has redesigned choices in the electronic health record to improve patient care. We recently implemented PainTracker,¹⁵ a patient-reported outcome system that focuses on a broad set of outcomes and causes of pain in a person's life to facilitate better health care. As a supplement to our parent grant (P30AG024968), we follow the explicit directives of NOT-AG-22-005 that task researchers with "Developing...strategies for collection of clinical pain data and for assessing, preventing, and managing pain in later life" (**Aim 1**) and the "elucidation of mechanisms underlying pain experience and its consequences in aging" (**Aim 2**). We will also compare rates of referrals and visits to mental health, physical therapy, and sleep medicine in a randomized trial that assigns older adults using long-term opioids to broader pain assessments.

2.2 Study Rationale

Use of point-of-care randomization within the electronic health record to learn if different survey assessments lead to different medical decisions and patient care pathways that will improve the health services received by long-term opioid therapy recipients. We develop strategies for comparison for collecting clinical pain data and for assessing, preventing, and managing pain in later life. Our intent is also to elucidate at the visit, some of the psychosocial factors underlying pain experience and its consequences in aging. We utilize the **UW PainTracker**,¹⁵ a brief assessment that **reframes** the patient visit around improving function and identification of correlates of pain intensity to broaden the discussion around patient needs to address chronic pain in an aged population.¹⁶

University of Washington (UW) PainTracker is a web-based, patient-reported outcomes tool.¹⁶ It tracks multiple outcomes relevant to the treatment of chronic pain: pain severity, general activity interference, enjoyment of life interference, sleep (initiating and maintaining), depression, and anxiety. PainTracker administers risk stratification tools once, including an Opioid Risk Tool, post-traumatic stress disorder (PTSD-PC), STOP sleep apnea screen, and fibromyalgia screen. New and returning patients are asked to complete the PainTracker assessment at least one week prior to their appointment. Between May and November 2012, PainTracker was deployed in 9 UW Neighborhood Clinics with access through a simple Epic® SmartSet, as part of a quality improvement program to better reduce opioid risk and lower high-dose use. This program included multimodal outcome tracking and encouraged reducing opioid doses below 120mg ME/day dose, documenting a treatment plan, and obtaining at least one urine drug screen per year. By 2014, these 9 clinics achieved a 57% overall reduction in opioid doses above 120 mg ME/day with the use of PainTracker. PainTracker broadens treatment targets and clinical conversations beyond a focus on pain intensity. As an example, we found in a separate sample of patients seeking outpatient pain treatment that were given PainTracker (n=2,824) that the number of post-traumatic disorder symptoms the patient has is positively related to pain intensity, pain interference in life activities and risk of opioid misuse (all $p < 0.001$).

Behavioral insights: We hypothesize that the aspects of the patient's health that are assessed and discussed at the visit affect the type of care received. Evidence for this comes from two sources in the field of psychology: 1) similarity research and 2) linguistic labels. Similarity is an organizing principle for statements and judgments about patients.^{23,24} "This patient is like ... [*some referent*]" is a type of task ubiquitous in medicine. For high scorers on the Current Opioid Misuse Measure, the measure promotes a response from the treating clinician that "this patient is behaving like a misuser of opioids". Whereas, broader assessments such as Pain Tracker may produce more varied similarity statements, such as "This patient is behaving like a person who has experienced psychological trauma". Further, linguistic labels may play a role in the stability of judgments about persons. Nouns such as "misuser" may have a stronger and more lasting effect on the person's identity than verbs (e.g., "misuses").^{25,26}

3. **STUDY DESIGN**

We will conduct a 9-month randomized trial where persons age 65 or older on long-term opioid therapy (N= 1451 persons within the Northwestern Medicine Chronic Opioid Use registry system with at least one primary care encounter in the past 12 months ending 8/08/2023) receiving care from 286 clinicians will receive either the 1) Current Opioid Misuse Measure alone (Standard clinical practice /Control) or 2) COMM + Pain Tracker (intervention). We will assess the primary outcome in the electronic health record: referral rate to non-opioid related care, which includes mental health, physical therapy and sleep medicine referrals. We will also

measure the rate of new starts on antidepressants. Secondary outcomes include: 1) clinician aggregate monthly milligram (mg) morphine equivalent (ME) and 2) benzodiazepine prescribing.

SELECTION AND ENROLLMENT OF PARTICIPANTS

3.1 Inclusion Criteria

Clinicians. The subjects involved in this trial are clinicians from outpatient clinics at Northwestern Medicine in Chicago, Illinois. Each study clinic is required to have an electronic health record (EHR) system in place and have its own physical building (as opposed to multiple clinics sharing the same space, such as the floor of a hospital, where interactions between providers assigned to different intervention groups would be more likely).

The target group of physicians is fully inclusive and representative. Clinicians will be eligible if they treat patients age 65 or older on long-term opioid therapy within the Northwestern Medicine Chronic Opioid Use registry system with at least one primary care encounter in the past 12 months ending 8/08/2023. We will request a waiver of consent for physician participation.

Patients. Patients will be eligible if they are ages 65 or older on long-term opioid therapy within the Northwestern Medicine Chronic Opioid Use registry system with at least one primary care encounter in the past 12 months ending 8/09/2022-8/08/2023. We will request a waiver of consent for patient participation.

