4.2.2 Enrollment, Baseline, and/or Randomization

Enrollment

This study involves a randomized trial with 286 clinicians to inform the best approaches to patient assessments for opioid at clinical visits. Long-term opioid recipients complete the Current Opioid Misuse Measure as standard clinical practice. PainTracker will appear as part of these required assessments randomly for half the patients of clinicians randomized to the intervention (COMM+PainTracker). If a waiver is granted, enrollment date (RCT implementation date) will be recorded for each clinic.

Assessments

Baseline: At baseline, we will assess clinician baseline prescribing monthly morphine milligram equivalents (MMEs), ICD-10 codes, and ordering data.

Enrollment and Randomization (Day 1). Demographics, inclusion/exclusion criteria, ICD-10 codes, and ordering data.

Intervention start (Month 1). ICD-10 codes, and ordering data, Pain Tracker/COMM completion rates, Referral rates to non-opioid care, adverse events

Continuously measured or monitored. ICD-10 codes, and ordering data, Pain Tracker/COMM completion rates, Clinician

monthly MMEs, Referral rates to non-opioid care, adverse events

Intervention end (Month 9): ICD-10 codes, and ordering data, Pain Tracker/COMM completion rates, Referral rates to non-opioid care, adverse events

Follow-up (Month 10-12): ICD-10 codes, ordering data, Clinician MMEs, Referral rates to non-opioid care.

Randomization

We will use cluster randomization at the physician level to avoid contamination that might occur if individual providers are randomized to multiple interventions. We will carry out block randomization of physicians with respect to historical referral rate (high vs. low) by using a random permutation of physician lists in the statistical computing language R. Patients of clinicians in the first half of the permuted list will receive the PainTracker survey intervention in addition to COMM. The second half will receive the control condition (COMM standard clinical practice). The same intervention (PainTracker survey) will be implemented throughout the 9 month study period. No intervention will occur during the 3 month follow-up period; it will be for outcomes assessment only.

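### The own-building criterion can limit contact between clinics only; physician-level randomisation mixes the arms within clinics, and the primary model states no clinic term to remove between-clinic noise

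*Combined protocol and SAP*

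**What the plan says.** Section 3.1 (Inclusion Criteria) requires each study clinic to "have its own physical building (as opposed to multiple clinics sharing the same space, such as the floor of a hospital". The reason given is that shared space is a setting "where interactions between providers assigned to different intervention groups would be more likely". The same section says "The target group of physicians is fully inclusive and representative", and section 3.2 lists no exclusions for clinicians.

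Section 4.2.2 sets the unit of allocation: "We will use cluster randomization at the physician level to avoid contamination that might occur if individual providers are randomized to multiple interventions". The method is "block randomization of physicians with respect to historical referral rate (high vs. low) by using a random permutation of physician lists", and the allocation rule is "Patients of clinicians in the first half of the permuted list will receive the PainTracker survey intervention in addition to COMM". Clinic is neither the unit of randomisation nor a blocking factor.

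Section 3 (Study Design) gives the size as 1,451 patients "receiving care from 286 clinicians will receive either the 1) Current Opioid Misuse Measure alone" or with PainTracker added. It does not mention the building rule beside that count.

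Section 7.4 analyses the primary referral outcome with a zero-inflated Poisson model for which no clinic term is stated. The spline model for morphine equivalents in the same section includes a clinic random effect.

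**The concern.** The reason given for the building rule suits a trial that allocates whole clinics. If all physicians in a building were in one arm, separating buildings would separate arms. Here physicians are permuted without regard to clinic, so the most direct route for contact between arms is between colleagues in the same clinic, and the rule does not touch it. Section 4.2.2 speaks of contamination only where one provider would be given several interventions. No section addresses contact between colleagues, although section 3.3 has clinicians told by email which assessments their patients will receive.

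Two things are at stake. First, a reader of section 3.1 may credit the design with more separation of the arms than it has. Any influence between colleagues would pull the estimated effect toward zero, and the plan does not say so. Second, mixing arms within clinics makes between-clinic variation in referral practice removable from the treatment comparison. The primary model as stated does not remove it.

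**Working it through.** **Plan's own figure (section 7.1).** Inputs: 150 clinicians per arm, 17 patients each (about 2,500 per arm), ICC 0.06, two-sided alpha 0.05, power 80%.
- Design effect = 1 + (17 − 1) × 0.06 = 1.96. Effective n per arm = 2,500 / 1.96 = 1,276.
- The detectable difference is 2.71 points from a 5% baseline and 3.58 points from 10%. These round to the stated 3 and 4, so the plan's figures reproduce to the whole point.

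**Mixing of arms within clinics.** Inputs: 286 clinicians (sections 3 and 4.2.2), half per arm (143), no clinic stratum. The referral-rate strata are ignored.
- Two colleagues in one clinic are in opposite arms with probability 143 / 285 = 50.2%.
- A clinic with k study physicians holds both arms with probability 1 − 2 × C(286 − k, 143) / C(286, 143).

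| k (assumed) | Both arms present |
|---|---|
| 2 | 50% |
| 3 | 75% |
| 5 | 94% |
| 10 | 99.8% |

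Treating each physician as an independent even chance, 1 − 2^(1 − k), gives 50%, 75%, 94% and 99.8%, so ignoring the strata matters little. The documents give neither the number of clinics nor their sizes.

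**What a clinic term could recover.** Inputs: 1,451 patients and 286 clinicians (section 3), so m = 1,451 / 286 = 5.07 patients per clinician and 1,451 / 2 = 725.5 patients per arm; ICC 0.06 (section 7.1); 5% versus 8%.
- Effective n per arm: n = 725.5 / [1 + (m − 1) × ICC].
- Power = Φ{[d − 1.96 √(2 p̄(1 − p̄)/n)] / √[(p₁(1 − p₁) + p₂(1 − p₂))/n]}, with d = 0.03 and p̄ = 0.065.

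A share of the ICC is assumed to lie between clinics and to be removed by the clinic term. The documents give no such split.

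| Share between clinics (assumed) | Remaining ICC | Design effect | Effective n per arm | Power |
|---|---|---|---|---|
| 0% | 0.060 | 1.244 | 583 | 54.7% |
| 10% | 0.054 | 1.220 | 595 | 55.5% |
| 50% | 0.030 | 1.122 | 647 | 59.0% |

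The gain is about 1 to 4 percentage points. The low starting value comes from the 1,451 patients in section 3, against about 2,500 per arm in section 7.1. That discrepancy is a separate matter and is not evidence for this point.

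**The case against.** The strongest reply is that the building rule still does something. Its wording concerns several clinics in one space and says only that contact there is more likely. Under physician randomisation about half of all physician pairs from different clinics are also in opposite arms, so keeping clinics in separate buildings can reduce between-arm contact. This stands. A reader might infer that the criterion gives no protection at all; the documents do not support that.

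A reader might also infer that the rule merely shrinks the trial. No section reports a clinic or clinician lost to it. Section 4.2.2 describes the randomised trial as having 286 clinicians, so that number may already be net of the rule. Any power loss from removed clinicians would rest on an invented fraction, and none is claimed here.

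Delivery also limits contamination. Under section 3.5, surveys go to patients through the portal and responses are visible to the patient's own doctor. Talking to a colleague does not give a control physician PainTracker results for his or her own patients. This bears on how large contamination could be, which the documents do not quantify. It does not show that contact within clinics was considered.

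Finally, deleting the rule or blocking by clinic would each increase the mixing of arms. That is correct, so neither is put forward as a necessary correction.

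**Conclusion.** The point holds in a limited form. The rationale in section 3.1 and the randomisation in section 4.2.2 do not fit together: the criterion can address contact between clinics, while contact within clinics is left open and unmentioned. Both arms will be present in most clinics with three or more study physicians (75% at three, 94% at five), on assumed clinic sizes.

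The practical consequence that can be put right concerns precision. Between-clinic variation stays in the primary comparison although the secondary model already carries a clinic effect. The gain from correcting this is modest, about 55% to 56-59% power for 5% versus 8%. It rests on section 3's patient and clinician counts, the plan's ICC of 0.06, and an assumed 10-50% of that ICC lying between clinics. The documents do not show that the trial has lost clinicians to the rule, nor that contamination will be large.

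**What to change.** **Primary model (section 7.4).** Add clinic as a random effect to the zero-inflated Poisson referral model, as the secondary model already has it, alongside the handling of clustering by physician. The cost is one model term; no extra patients or staff are needed.

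**Wording (sections 3.1 and 4.2.2).** Limit the building rationale to contact between clinics. State whether 286 is the count before or after the rule and, if before, how many clinicians it removes. State that physicians of both arms share clinics, so influence between colleagues would pull the effect toward zero. The cost is protocol text.

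**Optional.** Dropping the building rule could admit more clinicians, and blocking the randomisation by clinic could improve precision. Each accepts more mixing of arms in return, so these are design choices for the investigators to weigh.
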